6.1.1 Procedures for Discontinuation of Protocol –Specified Treatment Requirements and Follow-Up

For subjects who have been discontinued from protocol-specified treatment requirements but have not withdrawn consent, the following procedures will apply:

1. The subject will be asked to complete a discontinuation visit at the time of study discontinuation that will include a physical exam, lupus disease assessments as applicable (SLEDAI, BILAG, joint count), SLICC, LupusPRO, PGA, cbc, chemistry, C3, C4, anti-dsDNA and mechanistic studies.
2. If discontinuation is due to safety concerns, the subject will be given appropriate care under medical supervision, until the symptoms of any adverse event resolve or the subject's condition becomes stable.

6.2 Subject Withdrawal from the Study

When a subject is withdrawn from the study, protocol-specified treatment requirements are discontinued, and study-related visits, exams, procedures, assessments, tests and data collection are terminated. Individual subjects will be withdrawn from the protocol under the following conditions:

1. The subject withdraws consent.
2. The investigator believes it is in the best interest of the subject.
3. Subjects who are lost to follow-up will also be regarded as withdrawn from the protocol.

7. STATISTICAL ANALYSIS

7.1 Statistical Methods

The statistical analyses (*i.e.*, decision rules) have already been described above. In brief, we are testing the hypothesis that H_0 : response rate is $<20\%$ vs. H_A : response rate is $\geq 40\%$ using a Simon Two-Stage optimal design [39]. Stage 1 will enroll 13 subjects; if 3 or fewer respond, then the trial is stopped due to an inadequate response rate. If 4 or more subjects respond, then the trial continues to Stage 2, where 30 additional subjects are enrolled (total $n=43$). At the end of Stage 2, if 12 or fewer of the 43 subjects respond, then the treatment is declared inadequate. If at any point 13 or more subjects have responded, then the treatment will be considered for further testing. The procedure uses $\alpha=0.05$ and $\beta=0.20$. Under H_0 , the expected sample size is 20.6 and the probability of early termination is 75%. In order to operationalize the Simon Two-Stage rules, we will sequentially analyze and accumulate results on individual subjects as they complete Day 56 of the treatment period. Specifically, if 4 or more subjects have responded at any point in Stage 1, we will begin enrollment for Stage 2. Once a total of 13 subjects have responded the study will terminate.

7.1.1 Handling of Dropouts and Non-Evaluable Subjects

For the evaluation of efficacy using the Simon Two-Stage Optimal Design rule, any subject who is not evaluable or drops out from the study for any reason (including adverse events), will be replaced by a new subject. The subject being replaced will not be used in the analysis of efficacy. As noted elsewhere in this protocol, a subject will be considered “evaluable” for efficacy if he/she has complied with at least 80% of the prescribed medication dosing over the entire 56 days of medication administration ($<80\%$ is “not evaluable”). This “per protocol” rule has been implemented since this is a Phase II efficacy trial and the “intention-to-treat” principle does not apply. In order to account for a standard dropout rate of 20%, the potential maximum number of subjects to be enrolled will increase to 51 subjects.

For the evaluation of safety, any subject who is exposed to at least one dose of the medication will be included in all analyses of adverse events, even if this subject is replaced under the efficacy rule cited above.

The statistical analysis for the primary endpoint, therefore, is a straightforward calculation of percent change within each subject in anti-dsDNA antibody titer from baseline to 8 weeks. We have defined a clinically meaningful decrease in anti-dsDNA antibody titer to be a decrease in titer that is $\geq 35\%$; this is based on serologic data from a previous study comparing the efficacy of prednisone compared to placebo for disease flare prevention in serologically active, clinically stable SLE subjects [39]. For other secondary endpoints, descriptive statistics on continuous

measurements will include means, medians, standard deviations, and ranges, while categorical data will be summarized using frequency counts and percentages.

8. SAFETY MONITORING AND REPORTING (please also reference the Data Safety Monitoring Plan and sections 3.n-3.o of the MOOP)

This section defines the types of safety data that will be collected under this protocol and outlines the procedures for appropriately collecting, grading, recording and reporting that data. Serious adverse events and events requiring expedited review must be reported promptly (within 24 hours of the participating site PI becoming aware of the event) to the Sponsor Site PI and IND sponsor ([name], FIMR) who will inform the Safety Officer (SO) and NIAMS (through the KAI) within 48 hours. IND safety reports will be distributed to the participating site PIs and regulatory authorities (FDA) within 15 days. It is the Sponsor Site PI's responsibility to inform the Sponsor Site IRB at the FIMR. IRB reporting of SAEs and AEs will also be done as locally mandated. Information in this section follows guidelines and definitions from FDA-CFR Code of Federal Regulations Title 21, Part 312 Investigational New Drug Application found at <http://www.fda.gov/Drugs/DevelopmentApprovalProcess/HowDrugsareDevelopedandApproved/ApprovalApplications/InvestigationalNewDrugINDApplication/ucm226358.htm>. Data for this study will be collected on paper Case Report Forms (CRFs) that will be transmitted electronically to a central web based platform overseen by the Biostatistics Unit at the FIMR. Access to the database is restricted to the protocol Chair, Sponsor site PI and the personnel designated as data entry. The Co-Investigators, CSC, Office of Research Compliance and biostatisticians will have read only access. The web-based system is HIPAA compliant with strict password control and an automated database audit system.

The Office of Research Compliance (ORC) of NS-LIJ HS will be responsible for monitoring the study sites. The Sponsor site PI, [name], and the Steering Committee, comprised of Drs. [name], [name], [name] and [name] and [name] from the Biostatistics Unit, will oversee the conduct of the study. Principal Investigators at participating sites may also be part of the Steering Committee.

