soluble in methanol, ethanol, 2-propanol and propylene glycol. Tablets are available for oral administration as a light blue, capsule-shaped tablet with a clear film coating in 250 mg strength (as nelfinavir free base) and as a white oval tablet with a clear film coating in 625 mg strength (as nelfinavir free base). Each tablet contains the following common inactive ingredients: calcium silicate, crospovidone, magnesium stearate, hypromellose, and triacetin. The 250 mg tablet contains FD&C blue #2 powder and the 625 mg tablet contains colloidal silicon dioxide. Nelfinavir oral powder is available for oral administration in a 50 mg/g strength (as nelfinavir free base) in bottles. The oral powder contains the following inactive ingredients: microcrystalline cellulose, maltodextrin, dibasic potassium phosphate, crospovidone, hypromellose, aspartame, sucrose palmitate, and natural and artificial flavor. Nelfinavir has a plasma half life of approximately 3.5 to 5 hours and a steady state of the drug is achieved in 6 days [34-35]. It is metabolized by several cytochrome P-450 enzymes including CYP3A4, CYP2C19, CYP2C9, and CYP2D6. The recommended nelfinavir dose for treating adults with HIV or AIDS is 1250 mg (either five 250 mg tablets or two 625 mg tablets) twice daily or 750 mg (three 250 mg tablets) three times daily (Viracept Prescribing Information. Agouron Pharmaceuticals Inc, 2008). The research pharmacy at North Shore/LIJ Health System will obtain approved drug, nelfinavir/viracept, from Alexion Pharmaceuticals ([name]) through their specialty pharmaceutical distributor, Cardinal Health ([name]) The research pharmacy at North Shore/LIJ Health System will act as the central pharmacy for all sites in the study. As such, the central pharmacy will store the study drug and dispense drug to all participating sites as needed. Once a subject has been screened for the study, the site coordinator will contact the central study coordinator at the FIMR and an adequate amount of drug for that subject to complete the study will be shipped overnight from the central pharmacy to that site so that enrollment is not delayed. Unused or expired drug will be destroyed either at the local participating site or in the central pharmacy. Details for drug storage, maintenance and disposal specifications can be found in the Manual of Procedures.

4. KNOWN AND POTENTIAL RISKS and BENEFITS

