Treatment will be 750 mg nelfinavir thrice daily dosing (*t.i.d.*), if a given subject cannot tolerate this dose (*e.g.*, due to nausea), we will allow a step down to twice daily dosing (*b.i.d.*). Subjects and/or their insurance companies will not be charged for the nelfinavir; the study medication will be provided to all subjects free of charge. Compliance will be monitored by pill count – all evaluable subjects must maintain $\geq 80\%$ compliant (*i.e.*, ≥ 135 of 168 pills). While study endpoints will be determined immediately following treatment (8wk), durability will be assessed after a 4 week follow-up period. Because a Simon Two-Stage trial contains no placebo arm, we will be especially vigilant regarding safety. The Safety Officer and NIAMS have ultimate authority to address safety but we have incorporated clear stopping rules into the trial design (see section 5.4.2 for details).

**Figure 5. Study Design Flow Diagram
Simon Two-Stage: Nelfinavir in SLE (max 43 subjects)**

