6. STUDY WITHDRAWAL OR DISCONTINUATION

6.1 Discontinuation of Protocol-Specified Treatment Requirements

A subject is considered to have completed the study when he/she has completed the Day 84 visit. Protocol-specified requirements for the treatment of subjects will be discontinued for subjects under the following conditions:

1. Any protocol-specified treatment requirement will be discontinued immediately at any time during the study at the request of the subject.
2. Investigator will discontinue any protocol-specified treatment requirement if the subject's health, safety, and/or well-being is threatened.
3. Protocol-specified treatment requirements will be discontinued and replaced with appropriate therapy for any subject who experiences or requires any of the following:
 - An increase in dose of any concurrent SLE medications (including but not limited to corticosteroids, immunosuppressives, and/or immunomodulatory medications such as azathioprine, methotrexate, leflunomide, mycophenolate, and/or hydroxychloroquine) or addition of a new immunosuppressive medication (including cyclophosphamide or rituximab). *Note:* corticosteroids may be increased for a maximum of 2 days for reasons unrelated to SLE disease activity provided the last dose is taken more than 5 days prior to the day 56 assessments (section 5.3)
 - A grade 3 or higher NCI-CTCAE (version 4.0) adverse event that is considered to be related to study therapy during the course of the study. The exception to this will be hemoglobin levels where a grade 3 level of 8 may be acceptable. This will depend on the hemoglobin level at study entry and the investigator's assessment of relationship to study drug. A requirement for blood transfusion would be considered a stopping point.
 - Pregnancy
 - If a subject enrolls in a concurrent interventional trial.

In addition, subject non-compliance with treatment regimens or failure to keep appointments may disrupt protocol-specified treatment requirements and necessitate permanent discontinuation of treatment procedures at the discretion of the investigator.

Finally, protocol specified treatment requirements will be discontinued as a natural consequence in subjects who are withdrawn from the study per the study guidelines.

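### Section 7.1.1 replaces dropouts and poor compliers with no response table over all dosed subjects planned, and the fixed 135-of-168 compliance count in 5.1 does not fit the step-down to twice-daily dosing that 5.1 permits

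*Combined protocol and SAP*

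**What the plan says.** **Replacement.** Section 7.1.1 says that a participant who is non-evaluable or who "drops out from the study for any reason (including adverse events), will be replaced by a new subject". It adds: "The subject being replaced will not be used in the analysis of efficacy". The rule is openly labelled per-protocol, and the section says that intention-to-treat does not apply. To allow for 20% dropout, "the potential maximum number of subjects to be enrolled will increase to 51 subjects". The same section defines an all-dosed set (at least one dose), but only for adverse events.

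**Routes to removal.** Section 6.1 stops study treatment for, among other things, "An increase in dose of any concurrent SLE medications" or a related adverse event of grade 3 or higher. Section 5.4.1 discontinues subjects with new hyperglycemia.

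**Evaluability, two statements.** Section 7.1.1 counts a subject as evaluable if he or she has "complied with at least 80% of the prescribed medication dosing over the entire 56 days of medication administration", and presents this as a rule already given elsewhere in the protocol. Section 5.1 gives it as at least 80%, spelled out as at least "135 of 168 pills". The same paragraph says that if the thrice-daily dose is not tolerated, "we will allow a step down to twice daily dosing".

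**Decision rule.** Sections 5.1 and 7.1: stop if 3 or fewer of 13 respond; success needs 13 or more of 43. Results accumulate subject by subject, and the trial ends at the 13th response.

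**The concern.** In a single-arm trial the response rate is the whole efficacy result, and one responder decides each boundary (3 or 4 of 13; 12 or 13 of 43). Who enters the count therefore matters.

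Removal can be linked to outcome. A subject taken off treatment for a flare that needs more SLE medication may be less likely to respond. But the added corticosteroid may itself lower the anti-dsDNA titer. The stated error rates describe evaluable subjects and need not describe patients who start the drug. Without an all-dosed table, a reader cannot see how far replacement moved the rate, or in which direction.

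The compliance count is a separate defect. A fixed count built on thrice-daily dosing classes some fully adherent subjects as non-evaluable because they used an option the protocol allows. Section 7.1.1 may or may not do the same, so the analysis set is not uniquely defined.

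**Working it through.** **1. The plan's own figures.** Inputs from 5.1 and 7.1: n1 = 13, stop at 3 or fewer; n = 43, success at 13 or more; p0 = 0.20, p1 = 0.40.

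- Stage 1 stop: PET(p) = P(Bin(13, p) ≤ 3).
- Success: S(p) = Σ over x = 4 to 13 of P(Bin(13, p) = x) × P(Bin(30, p) ≥ 13 − x).
- At p = 0.20: PET = 0.747, S = 0.0496, expected N = 13 + 30 × (1 − 0.7473) = 20.6.
- At p = 0.40: S = 0.800.

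These match the stated 75%, 0.05, 20.6 and 0.80.

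**2. Sensitivity to removal.** Let P be the response rate in all treated subjects, d the fraction removed and q the response rate among those removed. The evaluable rate is pe = (P − d·q)/(1 − d). Take d = 8/51 = 0.157, the removal that the cap of 51 implies for 43 evaluable subjects. The documents give no value for q, so it is varied on both sides of P. For example, with P = 0.20 and q = 0.10, pe = (0.20 − 0.0157)/0.843 = 0.219.

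All-treated rate 20%:

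| q | pe | P(success) |
|---|---|---|
| 0.40 | 0.163 | 0.011 |
| 0.30 | 0.181 | 0.025 |
| 0.20 | 0.200 | 0.050 |
| 0.10 | 0.219 | 0.088 |
| 0 | 0.237 | 0.141 |

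The probability of stopping at Stage 1 is 0.852 at q = 0.40, 0.747 at q = 0.20 and 0.627 at q = 0.

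All-treated rate 40%: P(success) is 0.683, 0.747, 0.800, 0.844, 0.879 and 0.930 for q = 0.60, 0.50, 0.40, 0.30, 0.20 and 0.

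**3. Minimum success on two denominators** (Clopper-Pearson 95%, not adjusted for the two stages).

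- Evaluable: 13/43 = 30.2% (17.2 to 46.1%).
- All dosed, 51 dosed and no responder among the removed: 13/51 = 25.5% (14.3 to 39.6%).

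**4. The compliance count.** 3 doses × 56 days = 168, and 0.80 × 168 = 134.4, hence 135. So 168 is the thrice-daily dose count.

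- Twice daily from Day 1, perfect adherence: 2 × 56 = 112, and 112/168 = 66.7%. This fails 135.
- Step-down after x full thrice-daily days, perfect adherence: 3x + 2(56 − x) = 112 + x. This is 134 at x = 22 (fails) and 135 at x = 23 (passes).
- Section 7.1.1, if the prescribed dosing means the stepped-down regimen: 112/112 = 100%, evaluable (threshold 0.80 × 112 = 89.6, so 90).
- Section 7.1.1, if it means the original thrice-daily regimen: 112/168, not evaluable, in agreement with 5.1.

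On the stepped-down reading, if 5%, 10% or 20% of otherwise adherent subjects step down before 23 thrice-daily days (assumed; no rate is given), the two sections disagree on 0.05, 0.10 or 0.20 × 43 = 2.2, 4.3 or 8.6 subjects.

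**The case against.** **Per-protocol replacement is declared, and the trial is exploratory.** This stands. The plan calls the endpoint mechanistic, and its error rates are correct for the population it tests. That is why the Simon count should stay. But declaring the rule does not show how many subjects it removed, or why.

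**The two compliance statements may be one rule.** Section 7.1.1 refers back to a rule given elsewhere, which suggests the authors meant the same thing. A reader might infer a flat contradiction. The text supports less: the sections conflict on one reading of prescribed dosing and agree on the other. Even where they agree, the 135 count still excludes adherent subjects who step down early.

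**Evaluability could be chosen after titers are known.** A reader might infer this, but section 5.4.2(f) blinds investigators and study personnel to on-study autoantibody titers. Pill counts are taken from Day 7 to Day 56, before the samples are shipped and assayed. What remains is mainly a risk with those who run the sequential analysis in 7.1.

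**The tablet reading.** Section 3.2 describes a dose of "750 mg (three 250 mg tablets) three times daily", which makes 9 × 56 = 504 tablets. One might infer a threshold of 135/504 = 27%. That is implausible, because 5.1 states 80% and 168 together. Pills is loose wording for doses.

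**Samples from early discontinuations.** Section 6.1.1 collects anti-dsDNA at the discontinuation visit. It would be tempting to say these samples have no route to the laboratory, but handling is delegated to MOOP Appendix E, which is not among the documents.

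**Conclusion.** Two points hold.

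1. **Missing supportive result.** No all-dosed response result is planned, and the stated alpha and power refer to evaluable subjects only. This is a cheap improvement, not an error in the design. The documents do not support a claim that type I error is inflated. Success probabilities at a 20% all-treated rate lie on both sides of 0.05, from 0.011 to 0.141, and the direction is unknown. The ends are extreme cases (removed subjects responding at 40% or 0%). They rest on d = 8/51; with the plan's 20% dropout figure, the 0% case would give 0.186. The figures 13/43 and 13/51 are limiting cases, because the trial ends at the 13th responder and the actual denominator may be smaller.

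2. **A count that does not fit the permitted regimen.** As written, 5.1 makes a perfectly adherent subject non-evaluable after any step-down before 23 full thrice-daily days. This follows from the document's own numbers, reading 168 as doses. Whether 7.1.1 disagrees depends on a word it does not define. The figures of about 2, 4 or 9 disputed subjects need both the stepped-down reading and an assumed step-down rate.

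**What to change.** Keep the per-protocol Simon count for the go/no-go decision. In section 7.1.1:

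- **Pre-specify a supportive response table over all dosed subjects**, with an exact confidence interval, beside the evaluable result. Use the observed Day 56 titer wherever one exists, including for subjects under 80% compliance who completed. Count as non-responders only subjects with no Day 56 titer. List separately those still on treatment if the trial stops early.
- **Report the number of replacements and the reasons.**
- **State that alpha and power refer to evaluable subjects.**
- **Reconcile sections 5.1 and 7.1.1** on how compliance is counted after a step-down, and replace pills with the intended unit, before any titer result is seen. Which counting rule applies is for the sponsor to decide.

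**Cost.** One extra table and a wording change; the Simon boundaries and the evaluable sample size do not change. The all-dosed rate may be less favourable, and it is conservative for subjects without a Day 56 titer. The reconciliation can change who is evaluable, which is why its timing matters.

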
Objectives:
 
Primary objective: To demonstrate that the protease inhibitor nelfinavir, administered orally to SLE subjects with mild to moderately active disease, will decrease serum anti-dsDNA autoantibody binding by $\geq 35\%$.
 
Secondary objectives: 1) To assess the safety and tolerability of nelfinavir in SLE patients, 2) To assess the effect of nelfinavir on serum cytokine levels (IL-1, IL-6, and TNFα), 3) To assess the effect of nelfinavir on serum levels of C3, C4 and CRP, 4) To assess the effect of nelfinavir on the interferon signature, 5) To assess the effect of nelfinavir on binding of anticardiolipin antibodies, 6) To demonstrate that nelfinavir does not increase lupus disease activity and 7) To demonstrate that nelfinavir decreases disease activity.

Hypothesis:
 
Nelfinavir, a well-tolerated drug used to treat HIV, will be efficacious as a lupus therapeutic through inhibition of anti-dsDNA antibody binding to target organs and possibly through interfering with the formation of pro-inflammatory, DNA containing immune complexes, pro-inflammatory cytokines, and the IFN signature.

Study Arms:
 
A maximum of forty-three evaluable subjects will be required to assess the objective response rate ($>35\%$ reduction in dsDNA reactivity at 8 wks – end of treatment).
 
Stage 1: (maximum of 13 subjects enrolled)
 
 • If 3 or fewer respond, the trial is stopped due to an inadequate response rate • If 4 or more subjects respond, the trial continues to Stage 2 
Stage 2: (maximum of 30 additional subjects enrolled)
 
 • At end of Stage 2, if 12 or fewer of the 43 subjects respond, the treatment is declared inadequate • If 13 or more respond, then the treatment will be considered for further testing

Study Design:
 
This is an exploratory, multicenter, Phase IIa clinical trial with no placebo arm that utilizes the Simon Two-Stage trial design to investigate the immunomodulatory properties of nelfinavir, a protease inhibitor, in SLE patients with mild to moderate disease activity and elevated titers of anti-dsDNA antibodies. The safety, tolerability, and preliminary assessment of efficacy of nelfinavir in SLE patients will be explored.

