The Simon Two-Stage trial design limits exposure to study drug that is not effective and we believe that this trial design provides an efficient method for assessment of an FDA approved medication for HIV disease for another purpose. This study design does not have a placebo arm; all subjects will be dosed with nelfinavir 750 mg orally thrice daily. If the thrice daily dose is not tolerated, subjects will be allowed to decrease the dose to twice daily. For both stages of the trial the dosing period is 8 weeks followed by a 4 week observation period. A maximum of 13 subjects will be enrolled in the first stage of the trial followed by a maximum enrollment of an additional 30 in the second stage. The primary endpoint or "Response" is defined as a $\geq 35\%$ reduction in serum anti-dsDNA antibody titer from baseline values to end of treatment (8 weeks). This definition is based on established changes in anti-dsDNA titers in other lupus trials. We will test the null hypothesis that the true objective Response rate is $\leq 20\%$ (Inadequate Response Rate, which would not be clinically meaningful) versus the alternative hypothesis that the true Response rate is $\geq 40\%$ (Desirable Target Response Rate, Figure 5). Importantly, these Response Rates are consistent with results from other lupus clinical trials (e.g., immunosuppressives, steroids) where $\leq 20\%$ was considered not significant and $\geq 40\%$ was clinically meaningful. With a significance level of 0.05 and a power of 0.80, a maximum of 43 evaluable subjects (13 in Stage 1 plus 30 in Stage 2) will be required to assess the objective Response rate (Figure 5) [4]. From among the 13 subjects enrolled in Stage 1; if 3 or fewer objective Responses are observed, then the trial will be terminated (Figure 5A). If 4 or more objective Responses are observed in the first 13 subjects, however, the study will be expanded to enroll an additional 30 patients (Stage 2; Figure 5B). At the end of the study, if 13 or more Responses are observed, then the null hypothesis that the true response probability is $\leq 20\%$ will

be rejected and further investigation of nelfinavir in this patient population is warranted (Figure 5B) [4].

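### The enrolment maximum of 51 does not allow for the stated 20% dropout: 43 evaluable subjects need 54 enrolled, and 51 gives about 41 evaluable and power of about 0.78

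*Combined protocol and SAP*

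**What the plan says.** Section 5.1 sets the size of the trial: "With a significance level of 0.05 and a power of 0.80, a maximum of 43 evaluable subjects", made up of 13 in Stage 1 and 30 in Stage 2, to test a response rate of 20% against one of 40%.

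Section 7.1 gives the decision rules. For Stage 1: "Stage 1 will enroll 13 subjects; if 3 or fewer respond, then the trial is stopped due to an inadequate response rate". For failure at the end: "At the end of Stage 2, if 12 or fewer of the 43 subjects respond, then the treatment is declared inadequate"; the synopsis says the same ("if 12 or fewer of the 43 subjects respond, the treatment is declared inadequate"). For success: "If at any point 13 or more subjects have responded, then the treatment will be considered for further testing". Enrolment also ends once 13 subjects have responded.

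Section 7.1.1 replaces any subject who drops out for any reason or takes less than 80% of the prescribed doses, and leaves that subject out of the efficacy analysis. It then says that, to "account for a standard dropout rate of 20%, the potential maximum number of subjects to be enrolled will increase to 51 subjects".

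**The concern.** The target of 43 is a number of evaluable subjects, so an allowance for 20% loss must be found by dividing by 0.80. That does not give 51. Replacement does not make up the difference, because a maximum of 51 leaves room for 8 replacements, while 20% of 51 is about 10 losses.

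Two things are at stake. The first is power: the design only just reaches 0.80 at 43 evaluable subjects, so any shortfall takes it below the stated figure. The second is the wording of the failure rule, which is tied to exactly 43 subjects. A trial that ends at 51 enrolled with, say, 41 evaluable and 11 responders is not literally covered by the rule in Section 7.1 or the synopsis. If the boundary is unclear at that point, there is room to choose one after the data are known.

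**Working it through.** **Inputs.** Response rates 0.20 (null) and 0.40 (alternative), significance level 0.05, power 0.80 and 43 evaluable (Section 5.1); boundaries of at least 4 of 13 to continue and at least 13 for success, expected sample size 20.6 and early termination 75% under the null (Section 7.1); dropout 20% and maximum enrolment 51 (Section 7.1.1).

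**The plan's own design figures.** With X1 ~ Bin(13, p) responders in Stage 1 and X2 ~ Bin(n − 13, p) in Stage 2,

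P(success) = Σ over x = 4 to 13 of P(X1 = x) · P(X2 ≥ 13 − x).

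For n = 43 this is 0.0496 at p = 0.20 and 0.8002 at p = 0.40. Early termination under the null is P(X1 ≤ 3) = 0.747, and the expected sample size is 13 + (1 − 0.7473) × 30 = 20.58. The stated 0.05, 0.80, 75% and 20.6 all reproduce.

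**The enrolment figure.**

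- Required for 43 evaluable at 20% loss: 43/(1 − 0.20) = 53.75, so 54.
- Common short-cut: 43 × 1.2 = 51.6, which rounds up to 52. Rounding down gives 51, which is probably how the figure arose.
- Loss that 51 covers: (51 − 43)/51 = 8/51 = 15.7%.
- Evaluable from 51 at 20% loss: 51 × 0.80 = 40.8.

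**Effect of a shortfall.** Same formula, with the 13-responder rule kept:

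| Evaluable n | Type I error (20%) | Power (40%) |
|---|---|---|
| 43 | 0.0496 | 0.8002 |
| 42 | 0.0434 | 0.7911 |
| 41 | 0.0375 | 0.7798 |
| 40 | 0.0322 | 0.7658 |

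Lowering the boundary to 12 of 41 would bring power back to 0.808 but raise type I error to 0.067.

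**Averaging over random dropout.** Assume that each enrolled subject is lost independently with probability 0.20, unrelated to response. The documents do not state this. The evaluable number is then E = min(43, Bin(N, 0.80)) for a maximum of N enrolled:

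| Maximum N | Chance that E = 43 | Average power | Average type I error |
|---|---|---|---|
| 51 | 0.284 | 0.764 | 0.036 |
| 54 | 0.606 | 0.786 | 0.044 |
| 58 | 0.897 | 0.798 | 0.048 |

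**How often the failure rule would not literally apply.** This is the chance of passing Stage 1 and ending with fewer than 43 evaluable and fewer than 13 responders: P(pass Stage 1) × P(E < 43), minus the part of the average success probability that comes from E < 43. For N = 51:

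- At 40%: 0.8314 × 0.7161 − (0.7636 − 0.2839 × 0.8002) = 0.595 − 0.536 = 0.059.
- At 20%: 0.2527 × 0.7161 − (0.0359 − 0.2839 × 0.0496) = 0.181 − 0.022 = 0.159.

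For N = 54 the two figures are 0.026 and 0.086.

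**The case against.** The division is hard to dispute, but four points can be made against giving it weight.

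1. *The effect is small.* At a 40% response rate, once Stage 1 is passed, the chance of reaching 13 responders is 0.7798/0.8314 = 93.8% with 41 evaluable and 0.8002/0.8314 = 96.2% with 43. Type I error falls. The trial is exploratory and stops at Stage 1 about 75% of the time under the null. This stands, and it limits the seriousness of the point.

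2. *The replacement rule may govern.* Section 7.1.1 says that lost subjects are replaced and calls 51 a potential maximum; it does not say which prevails. If replacement prevails, 43 evaluable and power 0.80 are kept. That is a fair reading, but the sentence would still be wrong about what 51 allows for.

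3. *The failure rule is settled elsewhere.* Section 5.1 rejects the null if at least 13 responses are seen at the end of the study, without naming 43, so fewer than 13 does not reject. This largely stands: the intended outcome can be inferred, and rewording Section 7.1 and the synopsis is a tidy-up.

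4. *Enrolling 54 is not a full remedy.* It leaves a 39% chance of missing 43, with average power 0.786. That is true under the independence assumption, and the plan should say so if it adopts 54. It does not make 51 right.

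**Conclusion.** The concern holds. The figure of 51 does not match a 20% dropout rate around 43 evaluable subjects: the matching figure is 54, and 51 matches a loss of 15.7%. This follows from the plan's own numbers alone.

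The consequence is modest. Power is 0.780 instead of 0.800 if exactly 41 are evaluable, and 0.764 on average if dropout is independent at 20% and unrelated to response. Type I error falls to 0.038 and 0.036 respectively. These figures assume that 51 is a firm limit and that the 13-responder boundary is kept. The shortfall matters only in a trial that passes Stage 1 and reaches the limit without 13 responders. It should be corrected, but it does not undermine the design.

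**What to change.** Restate the sentence in Section 7.1.1 in one of two ways.

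- **Keep 51.** Say that it allows for 15.7% non-evaluable subjects, and that at 20% about 41 evaluable and power of about 78% are expected. If the averaged figure of about 76% is also given, state that it assumes independent dropout unrelated to response.
- **Change 51 to 54.** Show 43/0.80, and note that this gives 54 × 0.80 = 43.2 evaluable on average, a 61% chance of reaching 43, and average power of 0.786 under the same assumption. A sponsor who wants average power close to 0.80 would need about 58 (0.798).

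In either case, reword the failure rule in Section 7.1 and the synopsis as fewer than 13 responders among all evaluable subjects when enrolment ends. The success rule needs no change, and the boundary should not be lowered to fit a smaller number. It would also help to say whether the maximum or the replacement rule prevails.

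The first option and the failure-rule wording change text only; the second adds at most 3 subjects, or 7 if 58 is chosen. Each is a protocol amendment. It therefore needs ethics approval before use (Section 11.2) and written permission from the funder and sponsor (investigator signature page), at the lead site and at least 7 others (Section 1). It could be combined with the next amendment.
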